4. SAMPLE SIZE

Sample size estimates are based on other published data relating to the use of SASSAD in patients recruited in secondary care. Based on a minimum clinically relevant difference of 20% in the change in SASSAD score between the 2 groups, and assuming a mean baseline SASSAD score of 20 with a standard deviation in change scores of 10, a sample size of 310 children will provide 90% power, with a significance level of 5% allowing for an attrition rate of 15%.

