6. STRATA AND COVARIATES

6.1. Stratification variables

Randomisation is stratified by the following:

- Disease severity (baseline SASSAD ≥10 to ≤ 20, or SASSAD score >20)
- Recruiting centre

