6.2. Other covariates

In addition to the stratification variables, other covariates to be considered in a predictors of response model are:

- Age (continuous)
- Previous treatment history (see section 8.3)
- Water hardness at baseline (WHO classification, continuous).
- Sex
- Ethnicity
- Filaggrin status
- Income
- Time away from home (based on a cut off of >21 days).

In addition, the following baseline characteristics will be summarised:

Washing powder

- Fabric softener
- Bathing/showering frequency
- Swimming frequency
- Home ownership
- Allergy

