7. PLANNED SUBGROUP ANALYSES

A sub-group analysis will be conducted based on the presence or absence of mutations on the filaggrin gene (collected using spit samples). Mutations on the filaggrin gene have been associated with dry skin and may therefore be a useful predictor of treatment success. The planned subgroup analysis will only be performed on the primary outcome of change in SASSAD score. The p-value for the interaction will be reported.

Assuming that the presence of at least one mutation in the gene encoding filaggrin results in improved treatment response, a total of 90 children with at least one such mutation would be sufficient to detect a 30% difference between the treatment groups in the primary outcome, with 80% power, 5% significance (2 sided) and a standard deviation of 10. Allowing for a 20% drop out means that 120 children would need to carry the gene mutation. For 90% power this figure would be 145.

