10.3. Tertiary efficacy analyses

- 1) Speed of onset of benefit will be analysed in three ways. Firstly, the difference in the mean change in disease severity (SASSAD) at 4 weeks compared to baseline will be analysed using a t-test. Secondly, the final 4 week period (weeks 12 to 16) will be examined for the delayed treatment group using a single sample t-test. Finally daily bother scores from the daily symptom diaries for the first 4 weeks of the trial will be plotted for both groups.
- 2) Likely carry over effect will be examined graphically using the daily bother scores during the 16 week trial period for the immediate installation group. This information will be useful in planning the design of future trials in this area.
- 3) A responder will be defined as a 20% or 50% decrease in SASSAD score. Two logistic regression models will be used to investigate predictors of response as listed in section 6.2.

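### The tertiary predictors-of-response models cut the continuous SASSAD change at 20% and 50%, which loses power and makes the severity coefficient depend on the cut

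*Combined protocol and SAP*

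**What the plan says.** SAP 10.3 item 3 sets the outcome for the predictor analysis: "A responder will be defined as a 20% or 50% decrease in SASSAD score. Two logistic regression models will be used to investigate predictors". SAP 6.2 gives the candidate terms: "In addition to the stratification variables, other covariates to be considered in a predictors of response model are" age, previous treatment, water hardness, sex, ethnicity, filaggrin status, income and time away from home. The stratification variables in SAP 6.1 are recruiting centre and a two-level severity factor: "Disease severity (baseline SASSAD ≥10 to ≤ 20, or SASSAD score >20". Baseline SASSAD therefore enters twice, as the denominator of the responder definition and as a predictor.

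Elsewhere the score stays continuous. SAP 10.1 compares mean change with a t-test. For filaggrin, SAP 7 says "The planned subgroup analysis will only be performed on the primary outcome of change in SASSAD score", with an interaction p-value. No continuous version of the predictor model is planned, and no reason is given for dichotomising.

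SAP 3.3 makes the analysis tertiary and conditional on a beneficial effect. Protocol 6.3 lists it as exploratory, although protocol 10.4 places it among the secondary analyses. No power is stated for it.

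**The concern.** Two things are at stake if softening is found to help and readers then ask which children improve.

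First, a yes/no outcome discards how far each child moved, so a real predictor is easier to miss.

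Second, the bar moves with baseline. A 50% fall is 5 points for a child who starts at 10 and 20 points for a child who starts at 40. The severity coefficient then mixes any real difference in improvement with the way the bar was set, and the mixture differs between the two cuts. Adjusting for the severity stratum partly shields the other predictors but does not correct the severity coefficient itself. The SAP has no rule for two models that disagree.

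**Working it through.** **Inputs from SAP 4 and 7.** The target is "Based on a minimum clinically relevant difference of 20% in the change in SASSAD score between the 2 groups", "assuming a mean baseline SASSAD score of 20 with a standard deviation in change scores of 10". That is 0.20 × 20 = 4 points, with SD 10. Power is 90%, significance 5% and attrition 15%. The two-sided test is stated only for the filaggrin calculation and is assumed here.

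**Reproducing the plan's figure.** n per group = 2 × (1.960 + 1.282)² × 10² / 4² = 131.4, so 132 per group and 264 evaluable. 264 / 0.85 = 310.6, so 311 against the stated 310. It reproduces. Power at 132 per group is Φ(4 / (10 × √(2/132)) − 1.960) = Φ(1.29) = 0.901.

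**Assumptions not in the documents.** These are a predictor that splits the 264 children equally and is worth 4 points, the mean improvement c in its reference group, a baseline SD of 8, and the relation of change to baseline.

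**Power after the cut, everyone at baseline 20.** The cuts are then 4 and 10 points. Response rates are p0 = 1 − Φ((cut − c)/10) and p1 = 1 − Φ((cut − c − 4)/10). They are compared with the usual two-proportion formula, using pooled variance under the null. For c = 0 at the 50% cut:
- p0 = 1 − Φ(1.0) = 0.159 and p1 = 1 − Φ(0.6) = 0.274.
- Power = Φ((0.1156 − 1.960 × 0.0507) / 0.0502) = Φ(0.32) = 0.627.
- Loss = 0.901 − 0.627, about 27.5 points.

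| c | Power, 20% cut | Power, 50% cut | Loss (points) |
|---|---|---|---|
| 0 | 0.727 | 0.627 | 17.4; 27.5 |
| 2 | 0.734 | 0.674 | 16.8; 22.7 |
| 4 | 0.727 | 0.707 | 17.4; 19.4 |
| 6 | 0.707 | 0.727 | 19.4; 17.4 |

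For c from 0 to 10 the loss stays between 16.8 and 27.5 points. Restoring 90% power on the responder scale would take about 414 to 530 evaluable children.

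**Power with varying baselines.** Simulated trials of 264 children used baselines from 10 upward, with mean 20 and SD 8. With change unrelated to baseline or only additive, the loss was about 16 to 26 points. Across scenarios that also let improvement rise with baseline, linear models had 87–99% power and the cuts 68–88%, a loss of about 10 to 22 points. Taken together, the range is roughly 10 to 28. It is for an equal split. At a 30/70 split, linear power is already down to 0.846 and the loss is 19 to 32 points.

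**Severity: fixed baselines.** If mean improvement is 4 and SD 10 at every baseline b, the rate is 1 − Φ((f × b − 4)/10), where f is the cut:
- 20% cut: b = 12 gives 1 − Φ(−0.16) = 56%; b = 30 gives 1 − Φ(0.2) = 42%.
- 50% cut: b = 12 gives 1 − Φ(0.2) = 42%; b = 30 gives 1 − Φ(1.1) = 14%.

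If mean and SD both scale with baseline (0.2 × b and 0.5 × b), the rate is 50% at the 20% cut and 27% at the 50% cut for every b. The artefact is then zero.

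**Severity: varying baselines.** Mean improvement is 4 at baseline 20, the slope is points of improvement per baseline point, and the scatter about the line has SD 10. Responder rates are shown as ≤20 v >20:
- Slope 0: 36% v 18% at the 50% cut.
- Slope 0.2: 50% v 50% at the 20% cut, but 33% v 21% at the 50% cut, although severe children improve by about 5 points against about 2.
- Slope 0.5: 44% v 59% at the 20% cut, and 27% v 27% at the 50% cut.

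With the total SD of change held at 10 instead, a slope of 0.78 gives 17% v 32% at the 50% cut, so severe children look better.

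**The case against.** **Percentage response is the trial's own clinical scale.** The numbers needed to treat use 20% and 50% (protocol 10.3, SAP 10.1), the second secondary endpoint uses the same bands (SAP 3.2), and protocol 11.1 makes at least 50% improvement the primary effectiveness measure for the cost analysis. This stands. It is a reason to keep the responder results, but not to make them the only predictor models.

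**A reader might infer that severe children are bound to look like poor responders by construction.** The documents do not support that. It requires absolute change to be largely unrelated to baseline, and they say nothing about that relation. A minimum score of 10 at entry (protocol 7.1) makes some regression to the mean likely, and hence a positive slope. If the SD at week 12 stayed at the assumed 8, then 64 = 64 + 100 − 2 × slope × 64, so the slope would be 100/128 = 0.78, where the 50% cut favours severe children.

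**A reader might also put the loss at 29 points.** That figure belongs to an 8-point arm-by-factor interaction (88% to 59%). SAP 10.3 item 3 specifies no such interaction.

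**The linear model does not settle the severity question either.** In a regression of week-12 SASSAD, the baseline coefficient also reflects tracking and regression to the mean. This stands, and it limits how the remedy may be read.

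**Nothing confirmatory changes.** Primary inference is the continuous intention-to-treat comparison, and filaggrin is already tested on the continuous scale. This stands and sets the importance.

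**Conclusion.** The concern holds as a minor point. Dichotomising costs roughly 10 to 28 points of power for a 4-point, equal-sized factor among 264 children. The loss appeared in every scenario examined, but its size rests on assumed values for the control change, the baseline SD and the baseline–change relation. It is measured against a benchmark borrowed from the main comparison, since the SAP claims no power for these models.

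The sign of the severity coefficient cannot be predicted from the documents. It can be negative, nil or positive, and the 20% and 50% models can differ on the same data. The defect is that the coefficient depends on the cut, not that it is biased in a known direction. The primary, secondary and filaggrin results are untouched.

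**What to change.** In SAP 10.3 item 3, make the main predictor model one linear regression of week-12 SASSAD. Enter continuous baseline SASSAD in place of the two-level severity stratum, together with randomised arm, centre and the SAP 6.2 factors. Keep the 20% and 50% responder results as supportive or descriptive output, because they match the NNT and cost-effectiveness measures.

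Add a sentence that the baseline coefficient is not evidence that severe children respond differently to softening. If that question is wanted, pre-specify an arm-by-baseline term.

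The cost is SAP wording only, with no new data. The downside is that the main results come in SASSAD points rather than odds ratios of response, and the retained responder output largely covers that need.

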7.2 Exclusion criteria

- Children who plan to be away from home for >21 days in total during the 16-week study period. This has been deemed necessary in order to ensure adequate exposure to the intervention. We will also aim to ensure children do not have a planned holiday in the 4 weeks prior to their 12 week assessment visit.
- Children who have taken systemic medication (e.g. Cyclosporin A, methotrexate) or UV light for their eczema within the last 3 months because of their long lasting effects.
- Children who have taken oral steroids within the last 4 weeks, or who, as a result of seeing a healthcare professional, have started a new treatment regimen for eczema within the last 4 weeks.
- Families who already have a water treatment device installed, including ion-exchange softeners, polyphosphate dosing units or physical conditioners.

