12. ADDITIONAL GENETICS STUDY

12.1 The role of filaggrin gene mutations as a predictor of treatment response

Mutations in the gene encoding the skin barrier protein filaggrin have recently been shown to strongly predispose to eczema. Reduced filaggrin activity is associated with an abnormally dry skin and defective skin barrier. It is estimated that up to 50% of children with eczema may carry one or two mutations in the gene encoding filaggrin, which has the gene symbol *FLG* ¹⁸. Individuals carrying one null-allele for filaggrin make only 50% of the normal amount of filaggrin. Often these individuals have a mild form of ichthyosis vulgaris (a very dry skin) and are at risk for eczema. Individuals who have two null-alleles make no filaggrin and have a more severe form of ichthyosis vulgaris and are at greater risk of eczema ^{19,20}.

In light of this breakthrough in understanding eczema, we have formed collaborative links with the research team that first reported this association (lead by [name] at the Human Genetics Unit, University of Dundee). We plan to include filaggrin status as a possible predictor of treatment response in the current study. The mechanism of action by which water softeners improve eczema is currently unclear. Nevertheless, it seems intuitive to consider the possibility that a gene associated with dry skin may play an important role in predicting why some people with eczema are more affected by hard water than others.

For the sub-group analysis, study participants will be categorised into two groups according to filaggrin status:

Group 1: *FLG* +/+ (wild type) – control cohort

Group 2: *FLG* +/- (heterozygous for *FLG* null allele) and *FLG* -/- (homozygous for *FLG* null alleles)

This work will refine the phenotypic characteristics of filaggrin-deficient eczema, and will assess whether filaggrin is an important predictive factor in determining treatment

success.

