3.3. Tertiary Endpoints

If a beneficial effect is found the following tertiary analyses will be performed.

- 1) Speed of onset of benefit will be analysed in three ways. Firstly, the difference in the mean change in disease severity (SASSAD) at 4 weeks compared to baseline. Secondly, the final 4 week period (weeks 12 to 16) will be examined for the delayed treatment group. Finally the daily bother scores will be examined for the first 4 weeks of the trial for both groups.
- 2) Likely carry over effect will be examined using the full 16 week trial period for the immediate installation group. This information will be useful in planning the design of future trials in this area.
- 3) Predictors of response model, including baseline factors (see section 6.2)

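### SAP 10.3 item 3: the predictors-of-response models specify no randomised group, arm-by-factor term or analysis population, so for factors other than filaggrin they cannot separate prognosis from benefit

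*Combined protocol and SAP*

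**What the plan says.** SAP 10.3 item 3 states: "A responder will be defined as a 20% or 50% decrease in SASSAD score". It continues: "Two logistic regression models will be used to investigate predictors of response as listed in section 6.2".

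SAP 6.2 introduces its list with "In addition to the stratification variables, other covariates to be considered in a predictors of response model are" and names age, previous treatment history, baseline water hardness, sex, ethnicity, filaggrin status, income and time away from home. The stratification variables in SAP 6.1 are baseline SASSAD category and recruiting centre. Randomised group is on neither list. Protocol 6.3 and 10.4 describe the same kind of model and add no treatment term.

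The aim is framed as response to treatment. Protocol 12.1 says: "We plan to include filaggrin status as a possible predictor of treatment response in the current study". The one interaction in the plan is in SAP section 7, for filaggrin, on change in SASSAD.

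SAP 3.3 sets a condition: "If a beneficial effect is found the following tertiary analyses will be performed".

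On absence, SAP 6.2 lists "Time away from home (based on a cut off of >21 days", and protocol 7.2 excludes "Children who plan to be away from home for >21 days in total during the 16-week study period". Protocol 6.3 puts time away among the baseline factors. Protocol 5.5 and 9.1.2 have it recorded in diaries during the study.

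**The concern.** A child's SASSAD can fall by 20% without a softener. A model of who improved, with no contrast between arms in the effect of each factor, therefore answers a question about prognosis. Baseline severity is the plain example: children enter with active disease, and those with high scores may drift down in either arm.

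At stake is how factors such as water hardness, severity and previous treatment are described in the report. A factor that tracks improvement in both arms alike would be labelled a predictor of response, although it says nothing about who gains from softened water. A factor that truly modifies the effect could be diluted or hidden.

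Time away raises a separate difficulty. It is a post-randomisation exposure measure placed among baseline predictors, and it is split at the threshold already used to screen out planned absence.

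**Working it through.** **1. The plan's own size.** From protocol 10.2 and SAP section 4: difference 20% of 20 = 4 points, SD 10, 90% power, 5% significance (taken as two-sided), 15% attrition. Per arm, n = 2(1.960 + 1.282)² × 10²/4² = 131.3, so 132, or 264 in total. Then 264/0.85 = 311, against 310 stated, so the figure reproduces. Expected evaluable: 310 × 0.85 = 263.5. The predictor models have no stated size or power.

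**2. What each possible reading estimates.** Write improvement as a + t·T + b·X + g·T·X, with T the softener arm and X a factor. Here b is prognosis and g is effect modification. With 1:1 allocation, the slope on X is:
- arms pooled, with or without a main effect of arm: b + g/2
- softener arm only: b + g
- arm-by-factor term: g

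Only the last isolates g. Choosing the population, or adding arm as a main effect, does not.

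**3. Size, by simulation.** Assumptions, none from the documents except where stated: 264 children; a binary factor with prevalence 0.45; a 4-point mean treatment effect and SD 10 (the design values); 3 points of improvement under usual care without the factor; skewed baseline of at least 10 with mean 20; 1,500 runs per row. The responder cut is 20% (the 50% cut was not simulated). Entries are the percentage of runs with p < 0.05.

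| b, g (points) | Pooled | Pooled + arm | Softener arm only | Interaction, logistic | Interaction, linear |
|---|---|---|---|---|---|
| 0, 0 | 5.3 | 5.5 | 4.7 | 4.8 | 5.1 |
| 4, 0 | 67.5 | 69.7 | 37.5 | 4.0 | 3.9 |
| 6, 0 | 95.5 | 95.7 | 69.9 | 4.4 | 4.8 |
| 0, 6 | 42.8 | 42.5 | 75.3 | 50.7 | 68.5 |
| −3, 6 | 5.1 | 5.3 | 27.5 | 46.5 | 67.3 |

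Rows 2 and 3 are purely prognostic factors, and every model without an interaction flags them often. In row 4 the pooled model retains a diluted signal (median odds ratio 1.56, against 2.81 for the interaction). In row 5 prognosis and modification cancel and the pooled signal vanishes.

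**4. Precision of the interaction.** For a binary factor of prevalence q on the SASSAD change scale, SE = √[4·10²/(263.5q) + 4·10²/(263.5(1 − q))], and power = Φ(δ/SE − 1.96). The range 0.39 to 0.50 is taken from the filaggrin figures in protocol 12.1 and 12.4; 0.30 is an assumption.

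| q | SE | Power, 4 points | Power, 6 points | Detectable at 80% power |
|---|---|---|---|---|
| 0.30 | 2.69 | 32% | 61% | 7.5 |
| 0.39 | 2.53 | 35% | 66% | 7.1 |
| 0.50 | 2.46 | 37% | 68% | 6.9 |

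**5. False positives.** The seven factors without an interaction test are baseline severity, water hardness, age, previous treatment, sex, ethnicity and income; filaggrin makes eight. If the tests were independent at 5%, the chance of at least one false positive would be 1 − 0.95⁷ = 30% to 1 − 0.95⁸ = 34%.

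**6. Time away.** Protocol 7.2 excludes on planned absence over 16 weeks. SAP 6.2 uses the same number of days and gives no window. Provided the entry rule is applied, the upper class can hold only children whose actual absence exceeded their plans.

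**The case against.** The strongest reply is that this is a conditional, tertiary analysis, which protocol 6.3 calls exploratory, and that the SAP is silent rather than wrong. It gives no model formula, and the section 6.2 covariates are only to be considered. That stands: a reader may not infer that interactions are ruled out, only that none is specified. The silence still matters, because step 2 shows that the other readings of the text leave the problem in place.

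Several stronger readings are tempting and are not supported:
- **That filaggrin cannot be assessed as a modifier.** SAP section 7 gives it an interaction test on continuous change.
- **That the models detect effect modification no better than chance.** This holds only where effects offset (row 5); otherwise a diluted part comes through (row 4).
- **That predictors would be reported even if the softener does nothing.** SAP 3.3 runs the models only after a beneficial effect is found. This limits the harm, but a positive main result does not separate prognosis from modification.
- **That dichotomising costs a fixed 36% of the information.** That figure is for a median split of a normal outcome, and nothing places either cut at the median. The 20% and 50% cuts match the numbers needed to treat in SAP 10.1, and 50% is the main effectiveness measure in protocol 11.1, so they have a reason to stay.
- **That the >21-day class will be nearly empty.** The entry rule concerns planned absence, and the documents give no distribution of actual absence. It may be sparse; no more can be said.
- **That the results would decide who is advised to buy a unit.** No section uses them so, and purchase is offered to all participants.

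It is also fair that including absence is deliberate (protocol 5.5). The objection that remains is to listing it as a baseline factor and to the choice of cut.

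**Conclusion.** The point holds for the factors other than filaggrin. Carried out as described, the two logistic models would present prognostic factors as predictors of response and could not isolate effect modification. Under the assumptions in step 3, a 4-point prognostic factor with no modification is flagged in about 68% of pooled analyses and 38% of softener-arm analyses, against 4% for the interaction test. These percentages move with the assumed prevalence, effect sizes and baseline distribution; the algebra in step 2 does not depend on those values.

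The consequence is confined to the interpretation of a tertiary analysis that runs only after a benefit is found. The primary inference is unaffected. Time away is a smaller, related point: a post-randomisation measure is listed as a baseline factor, with a cut that may leave few children in the upper class.

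**What to change.** Amend SAP 10.3 item 3 and section 6.2 as follows:

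- State that both arms are analysed.
- For each baseline factor, fit a linear model for week-12 SASSAD (or its change) with baseline SASSAD, centre, arm, the factor and the arm-by-factor interaction. For severity, the factor is baseline SASSAD itself.
- Report interaction estimates with 95% confidence intervals, labelled exploratory and without multiplicity control. Describe main effects as prognostic.
- Keep the 20% and 50% logistic models, with the same terms, as supportive.
- Analyse nights away as a continuous post-randomisation exposure measure, separately from the baseline predictors.

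If interactions are not wanted, the minimum is to rename the models prognostic.

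The cost is wording only, on data already collected. The downside is low precision: an interaction SE of about 2.5 points, with power of about 35–37% for a 4-point and 66–68% for a 6-point interaction at prevalence 39–50%. There is also the 30–34% chance of at least one false-positive interaction, which is why the exploratory label is needed. Baseline adjustment may narrow the intervals, but the documents give no baseline-to-week-12 correlation from which to say by how much.
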